4 INVESTIGATIONAL PLAN

4.1 Study Design

We propose to conduct a multi-arm, open-label, phase 2 basket trial investigating the efficacy and safety of copanlisib in combination with fulvestrant in patients with selected HR+ advanced or metastatic solid cancers, harboring PI3K or PTEN alterations including ovarian cancer (cohort 1), endometrial cancer (cohort 2), and breast cancer (cohort 3). Cohort 3 will be enriched to include at least 7 patients naïve to any PI3Ki in Stage 1 and also in Stage 2.

Proprietary Information of MD Anderson

Protocol 2020-1241

19 October 2022

and will be contacted by telephone every 12 weeks (± 14 days) for survival status until death, withdrawal of consent, or lost to follow-up.

Exploratory biomarker studies using pre-treatment, on-treatment, and post-progression tumor biopsy tissues and serially collected blood liquid biopsies will investigate clonal evolution, and mechanisms of innate and adaptive resistance.

The study will consist of a screening/baseline phase, treatment phase, safety follow-up, follow-up visits, and survival follow-up.

4.1.1 Screening/Baseline Phase

Written informed consent is required before performing any study-specific tests or procedures. The signing of the informed consent form (ICF) can occur outside the 28-day screening period. All screening evaluations must be completed and reviewed to confirm that patients meet all eligibility criteria before study entry. Results of the standard of care (SOC) tests or examinations performed before obtaining informed consent and within 28 days prior to study entry may be used for screening assessments rather than repeating such tests. The investigator or designee will maintain a screening log to record details of all patients screened and to confirm eligibility or record reasons for screening failure, as applicable.

[figure not shown]
ICFs for enrolled patients and for patients who are not subsequently enrolled will be maintained at the study site.

The use of remote consenting to obtain informed consent from clinical trial participants using paper or electronic consent forms is allowed in this study.

Evaluations for PI3K and/or PTEN alterations and hormone receptor status will be performed by a U.S. Clinical Laboratory Improvement Amendments (CLIA)-certified and College of American Pathologists-accredited clinical laboratory.

Baseline assessments will be performed within 28 days of study treatment initiation unless specified otherwise.

4.1.2 Treatment Phase

Proprietary Information of MD Anderson

Protocol 2020-1241

19 October 2022

treatment in the opinion of the investigator, the patient is clinically asymptomatic, and continuation of study treatment is approved by the sponsor.

Assessments will be performed at the time points specified in the Schedule of Assessments (Appendix A).

4.1.3 Safety Follow-Up

The safety follow-up visit should be conducted 30 (+ 5) days after the last dose of study treatment or before the initiation of a new anticancer therapy, whichever comes first. AEs that occur prior to the safety follow-up visit will be recorded as per the NCI Adverse Events Recording Guidelines for Phase II trials. Patients with an AE of > Grade 1 will be followed until the resolution of the AE to ≤Grade 1 or baseline. Serious AEs (SAEs) that occur within 30 days of EOT should also be followed and recorded.

4.1.4 Follow-Up Visits

Patients who discontinue study treatment for a reason other than disease progression will move into the follow-up phase. Patients will be monitored for disease status by tumor imaging (CT scan or MRI, as appropriate) every 8 weeks (± 7 days) until PD, death, initiation of new anticancer therapy, withdrawal of consent, or lost to follow-up.

4.1.5 Survival Follow-Up

Patients who experience confirmed disease progression or initiate a new anticancer therapy will move into the survival follow-up phase. Patients will be contacted by telephone every 12 weeks (± 14 days) for survival status until death, withdrawal of consent, or lost to follow-up.

4.1.6 Pharmacodynamic Assessments

In patients with accessible tumor, tumor biopsies may be obtained at Screening (within 28 days of Cycle 1 Day 1) on-treatment after fulvestrant and copanlisib administration on Cycle 2 Day 1, and at EOT. Tumor biopsies will be optional but encouraged, especially in patients with a response or prolonged disease control. Tumor biopsies will be used to evaluate genomic biomarkers of response and intrinsic and adaptive resistance.

Mandatory blood samples to isolate plasma ctDNA will be collected at pre-treatment (Day -28 to Day 1 of Cycle 1), on-treatment (pre-dose -at the same time as the on treatment biopsy- on Cycle 2 Day 1 as well as at the first two restaging visits), and post-treatment at EOT. Tissue and plasma ctDNA will be used to evaluate molecular and genetic biomarkers of response and resistance to study treatment. ctDNA analyses may include genomic profiling, concordance of ctDNA and tumor findings, and evolution of genomic profile with treatment upon serial samples. Genomic DNA will be used for the determination of somatic changes in the tumor and genomic variations that may affect the response. Since the ctDNA and biopsy analyses are performed exclusively for research purposes, the results will be used to increase the clinical experience to help move the field forward, but they will not be made available to patients.

Proprietary Information of MD Anderson

Protocol 2020-1241

19 October 2022

4.1.7 Removal of Patients from the Study

Every effort within the bounds of safety and patient choice should be made to have each patient complete the treatment period of the study. Patients who have treatment discontinued due to PD may be treated with any additional therapy deemed appropriate by the investigator. Patients with disease progression per RECIST can continue on therapy for clinical benefit if deemed appropriate by the investigator.

Patients may be discontinued from the study for any of the following reasons:

- Investigator recommends discontinuation and documents the reason(s)
- There is a need for any treatment not allowed by the protocol
- Patient's decision to withdraw consent or discontinue for any reason
- There is an unacceptable AE thought to be related to study medication

Any patient who discontinues during the treatment period should return to complete safety and disease assessments (see **Appendix A: Schedule of Assessments**).

4.1.8 COVID-19 Pandemic Study Procedures

During the COVID-19 pandemic, alternative methods for conducting study assessments should be considered when compliance, feasibility, and safety could be assured. These methods may include telemedicine visits (e.g., via telephone/video using compliant video-conference tools as permitted by health authority regulations) and use of primary care centers and local laboratories for blood draws and imaging/radiographs.

[figure not shown]
If alternative methods are used, local laboratory reference ranges will be documented. Local laboratory test results, laboratory accreditation, and reports of tumor assessments should be retrieved and documented in the patient's study records. The principal investigator (PI)/treating physician will review labs, determine clinical significance and sign/date results.

The use of remote consenting to obtain informed consent from clinical trial participants using paper or electronic consent forms is allowed in this study.

5 STUDY POPULATION

5.1 Patient Population

The study population will consist of subjects with selected HR+ (ER+ or/and PR+) advanced or metastatic solid tumors with PI3K (*PIK3CA*, *PIK3R1*) and/or *PTEN* alterations. Patients must have no available standard therapy known to prolong survival or are not candidates for such a therapy.

[figure not shown]

Proprietary Information of MD Anderson

Protocol 2020-1241

19 October 2022

all patients complete the first 28 days, the study will advance to Part 2 (dose expansion), provided there is no more than 1 DLT observed. Patients will be considered evaluable for Part 1 once they have completed at least 1 cycle of treatment or they experience DLTs in the first treatment cycle.

[figure not shown]

Cohort 1: Ovarian cancer (ER+ and/or PR+, PI3K or PTEN altered).

Cohort 2: Endometrial cancer (ER+ and/or PR+, PI3K or PTEN altered).

Cohort 3: Breast cancer (ER+ and/or PR+, PI3K or PTEN altered). Cohort 3 will be enriched to include at least 7 patients naïve to any PI3Ki in Stage 1 and also in Stage 2.

Patients will be considered evaluable for Part 2 once they have completed at least 2 cycles of treatment and have at least one efficacy assessment.

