2 STUDY OBJECTIVES

The objective of this phase 2 basket study is to evaluate the efficacy and safety of copanlisib in combination with fulvestrant administered to subjects with selected ER+ and/or PR+ advanced or metastatic solid tumors with PI3K and/or PTEN alterations

2.1 Part 1: Dose confirmation:

Primary Objective:

- To evaluate the safety, tolerability, and DLTs of copanlisib 60 mg administered IV on Days 1, 8 and 15 in combination with fulvestrant 500 mg administered IM on Day 1 and Day 15 of Cycle 1, and then on Day 1 of each subsequent 28-day cycle to confirm the RP2D of the combination therapy.

Secondary objectives:

- To assess the efficacy of copanlisib administered in combination with fulvestrant as outlined in Part 2 by evaluating the ORR.
- To evaluate additional efficacy measures such as PFS and OS of copanlisib in combination with fulvestrant.

Exploratory Objective:

- To investigate clonal evolution, and mechanisms of resistance using tissue and liquid biopsies utilizing ctDNA as outlined in Part 2.

2.2 Part 2: Dose expansion:

Primary objective:

- To assess the efficacy of copanlisib administered in combination with fulvestrant as outlined above by evaluating the ORR. Patients enrolled for Part 1 will be included in this efficacy analysis.

Secondary Objectives:

- To evaluate additional efficacy measures such as PFS and OS of copanlisib in combination with fulvestrant.
- To evaluate the safety and tolerability of copanlisib in combination with fulvestrant.

Exploratory Objective:

- To investigate clonal evolution, and mechanisms of resistance using tissue and liquid biopsies utilizing ctDNA.

Proprietary Information of MD Anderson

Protocol 2020-1241

19 October 2022

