- **The following event is classified as a DLT:**

- If a full cycle of copanlisib (3 doses) will not be completed due to any study intervention-related AE, the AE is considered as a DLT
- A delay of over 1 week in initiating Cycle 2 of copanlisib and/or fulvestrant treatment occurs secondary to any study drug related AE, the AE will be considered a DLT
- Death not clearly attributed to underlying disease or alternative cause

Note: Allergic reactions leading to discontinuation of study interventions will not be considered as a DLT and participant will be replaced.

3.3 Exploratory endpoints:

Biomarker-based studies will be performed using tumor tissue and liquid biopsies to assess clonal evolution, and mechanisms of innate and adaptive resistance.

Tumor biopsies, if medically feasible, will be obtained at screening (within 28 days of Cycle 1, Day 1) on-treatment after fulvestrant and copanlisib administration on Cycle 2 Day 1 and at EOT. Biopsies will be optional but encouraged, especially in patients with a response or prolonged disease control. Examples of studies include identification of genomic biomarkers of response and intrinsic or adaptive resistance by whole exome, targeted NGS, and Nanostring DSP or other similar methods.

Proprietary Information of MD Anderson

Protocol 2020-1241

19 October 2022

[figure not shown]
Mandatory blood samples to isolate plasma ctDNA will be collected at pre-treatment (Day -28 to Day1 of Cycle 1), on-treatment (pre-dose -at the same time as the on treatment biopsy- on Cycle 2 Day 1 as well as at the first two restaging visits), and post-treatment at EoT.

Plasma ctDNA samples will be used to evaluate changes in ctDNA quantity and clonal evolution by selected molecular methods that may include targeted NGS, methylation sequencing, and droplet digital polymerase chain reaction.

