6.3.1 Copanlisib toxicity management

Table 5: Management of Nausea/vomiting

Toxicity	Action to be Taken
CTCAE Grade 1	No change in dose
CTCAE Grade 2	Hold* until \leq Grade 1. No change in dose
CTCAE Grade 3	Hold* until \leq Grade 2. Resume at one dose level lower, if indicated.**
CTCAE Grade 4	Off copanlisib treatment

*Patients requiring a delay of >2 weeks may go off protocol therapy.
**Patients requiring >2 dose reductions should go off protocol therapy.

Recommended management: Antiemetics

Table 6: Management of Diarrhea

Toxicity	Action to be Taken
CTCAE Grade 1	No change in dose
CTCAE Grade 2	Hold* until \leq Grade 1. No change in dose
CTCAE Grade 3	Hold* until \leq Grade 2. Resume at one dose level lower, if indicated.**
CTCAE Grade 4	Off copanlisib treatment

*Patients requiring a delay of >2 weeks may go off protocol therapy.
**Patients requiring >2 dose reductions should go off protocol therapy.

Proprietary Information of MD Anderson

Protocol 2020-1241

19 October 2022

Recommended management: Loperamide antidiarrheal therapy

Dosage schedule: 4 mg at the first onset, followed by 2 mg with each loose motion until diarrhea-free for 12 hours (maximum dosage: 16 mg/24 hours)

Adjunct anti-diarrheal therapy is permitted and should be recorded when used.

Table 7: Management of thrombocytopenia

Toxicity	Action to be Taken
CTCAE Grade 1	No change in dose
CTCAE Grade 2	No change in dose
CTCAE Grade 3	Hold* until \leq Grade 1. Resume at one dose level lower, if indicated. **
CTCAE Grade 4	Off copanlisib treatment

*Patients requiring a delay of >2 weeks may go off protocol therapy.

**Patients requiring >2 dose reductions should go off protocol therapy.

Table 8: Management of Neutropenia

Toxicity	Action to be Taken
CTCAE Grade 1	No change in dose
CTCAE Grade 2	No change in dose
CTCAE Grade 3	Hold* until \leq Grade 2. Resume at one dose level lower, if indicated. **
CTCAE Grade 4	Off copanlisib treatment

*Patients requiring a delay of >2 weeks may go off protocol therapy.

**Patients requiring >2 dose reductions should go off protocol therapy.

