6.3.1.1 Dose Modification Rules for Transient Post-Infusion Hyperglycemia

Patients who develop transient post-infusion glucose >250 mg/dL after study drug administration may continue treatment. However, the next infusion must be delayed until the patient's pre-infusion glucose levels return to <160 mg/dL (fasting) or <200 mg/dL (non-fasting). Guidelines for the management of transient glucose increases are given in the tables below. The continuing occurrence of post-infusion blood glucose >500 mg/dL, based on repeated laboratory analysis despite optimal glucose-lowering therapy after 2 infusions of copanlisib, will require dose reduction by one dose level.

- Further dose reduction (where appropriate per study design/population) is allowed as long as discontinuation criteria were not met.
- Dose re-escalation is allowed when a patient has achieved controlled glucose levels per investigator's judgment.

Proprietary Information of MD Anderson

Protocol 2020-1241

19 October 2022

- Persistent occurrence of post-infusion blood glucose >500 mg/dL based on laboratory analysis, which occurred at the lowest dose level despite optimal glucose-lowering therapy (after at least one cycle of treatment) with the consultation of a diabetes specialist requires permanent discontinuation of the study drug.

Table 9: Management of post-infusion glucose increase

Toxicity	Action to be Taken
Glucose increase of CTCAE Grade 1 (abnormal glucose level above baseline with no medical intervention)	
• Continue study treatment
Glucose increase of CTCAE Grade 2 (change in daily management, from baseline for a diabetic; oral antiglycemic agent is initiated; workup for diabetes)	
• Hydration as clinically indicated• When planning next infusion prophylaxis with oral glucose-lowering medication per local SOC is recommended• Consultation with an endocrinologist for diabetic patients is recommended
Glucose increase of CTCAE ≥Grade 3 (insulin therapy initiated; hospitalization or urgent intervention indicated; life-threatening consequences)	
• Hydration as clinically indicated (orally, IV)• Insulin therapy per local SOC• When planning next infusion consider prophylaxis with oral glucose-lowering medication per local SOC• Consultation with an endocrinologist is recommended

Table 10: Management of Transient Glucose Increase on the Day of Copanlisib Infusion

Criteria	Recommendations

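### Part 1 can count a patient as DLT-free at copanlisib 60 mg although toxicity that is not a DLT led to a lower dose within Cycle 1

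*Combined protocol and SAP*

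**What the plan says.** Section 2.1 gives the Part 1 objective: "To evaluate the safety, tolerability, and DLTs of copanlisib 60 mg administered IV on Days 1, 8 and 15" with fulvestrant, "to confirm the RP2D of the combination therapy". The decision rule is in the readable Part 1 text of Section 5, ahead of the inclusion criteria: "the study will advance to Part 2 (dose expansion), provided there is no more than 1 DLT observed". The next sentence defines who counts: "Patients will be considered evaluable for Part 1 once they have completed at least 1 cycle of treatment", or have a DLT in the first cycle. Neither sentence mentions the dose received.

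Section 3.2 and the synopsis contain one DLT clause on dose delivery: "If a full cycle of copanlisib (3 doses) will not be completed due to any study intervention-related AE", the event is a DLT. The parenthesis defines a full cycle by number of infusions. A delay of more than a week in starting Cycle 2 because of a related event is also a DLT. A dose reduction is not on the list.

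The dose-modification rules are in Section 6. For Grade 3 nausea or vomiting and Grade 3 diarrhea, Tables 5 and 6 call for a hold and then "Resume at one dose level lower, if indicated". For glucose, Section 6.3.1.1 says that values above 500 mg/dL which keep occurring despite optimal glucose-lowering therapy, "after 2 infusions of copanlisib, will require dose reduction by one dose level". No readable text suspends these rules during Cycle 1.

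**The concern.** The DLT count is the only readable criterion for moving from Part 1 to Part 2, and it should say whether patients can be kept on 60 mg for a cycle. If a patient leaves 60 mg because of toxicity and no DLT is recorded, that toxicity is absent from the numerator while the patient stays in the denominator as a success at 60 mg. The error can only favor passing. Part 2 would then open at a dose that some Part 1 patients had already left in their first cycle, and Section 2.2 carries Part 1 patients into the Part 2 response analysis.

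**Working it through.** The plan gives no figure to reproduce: the Part 1 sample size, a target DLT rate and operating characteristics are not readable. The check is therefore to trace the rules, followed by an illustration on stated assumptions.

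**Route 1, diarrhea (nausea and vomiting work the same way).**
1. Related Grade 3 diarrhea starts on Day 2, is down to Grade 2 or lower by Day 5 and to Grade 1 by Day 8. Section 3.2 exempts Grade 3 diarrhea that falls to Grade 2 or lower within 3 days of standard therapy. No DLT.
2. By Day 8 the hold conditions of Table 6 and Section 6.2 are met. Table 6 allows one dose level lower on Days 8 and 15.
3. Three infusions are given, so the dose-delivery clause is not triggered.
4. The cycle is complete: evaluable, DLT-free.

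**Route 2, glucose.**
1. Post-infusion glucose exceeds 500 mg/dL after Day 1 and again after Day 8 despite optimal therapy, each time settling within 7 days and in time for the next infusion. Table 9 sets the grade by the intervention needed, so this can be Grade 3. Section 3.2 exempts Grade 3 hyperglycemia of 7 days or less. No DLT.
2. Section 6.3.1.1 then requires a reduction, which falls on Day 15.
3. Three infusions, the last below 60 mg: evaluable, DLT-free.

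**Triggers that do not open the gap.**

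| Reduction trigger | Why it is outside |
|---|---|
| Infusion missed for a related event | DLT under the three-infusion clause |
| Related Grade 3 skin toxicity (6.3.1.4) | DLT as a Grade 3 non-hematological event with no exemption |
| Related Grade 3 hypertension (6.3.1.3) | Same |
| Related Grade 2 non-infectious pneumonitis (6.3.1.6) | Named as a DLT |
| Grade 3 neutropenia (Table 8) | Mostly outside: blood counts fall on infusion days, the visit window is ±2 days, and the hold will often cost an infusion, which is then a DLT |

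**Illustration only.** Let p be the true DLT rate, q the further proportion reduced in Cycle 1 without a DLT, and n the number of evaluable patients. All three are assumptions. With X binomial(n, π), P(pass) = P(X ≤ 1) = (1−π)^n + nπ(1−π)^(n−1).

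- As written, π = p.
- Reduced patients not evaluable and replaced: π = p/(1−q).
- Reduced patients counted against the dose: π = p+q.

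For n = 6, p = 0.15, as written: 0.85^6 + 6(0.15)(0.85^5) = 0.377 + 0.399 = 0.776.

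| n | p | q | As written | Replaced | Counted against |
|---|---|---|---|---|---|
| 6 | 0.15 | 0.05 | 0.776 | 0.758 | 0.655 |
| 6 | 0.15 | 0.15 | 0.776 | 0.713 | 0.420 |
| 10 | 0.15 | 0.05 | 0.544 | 0.516 | 0.376 |
| 10 | 0.15 | 0.15 | 0.544 | 0.451 | 0.149 |

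The effect depends mainly on q, for which the documents give no value, and on how the reduced patient is classed.

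**The case against.** The strongest reply is that the DLT list already does most of this work. Most toxicities that lead to a reduction are DLTs in themselves, and a lost infusion is one too. That stands, and it confines the point to patients who received all three infusions.

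Second, most reductions are optional, since Tables 5 to 8 leave them to clinical indication, and an optional reduction does not prove that 60 mg was intolerable. This is fair, but the patient still did not receive the regimen under confirmation. The glucose reduction is not optional, although it has strict conditions and in Cycle 1 can affect only Day 15.

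Third, a full cycle might be taken to mean full dose. The parenthesis, which counts doses, makes that reading hard to sustain.

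Fourth, Section 6.3 requires dose modifications to be documented, and Section 8.1 reports dose reductions. Both are true, but no readable text brings that report into the decision to open Part 2.

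Fifth, text just before the decision rule, parts of Section 6 and most of Section 8 cannot be read. A dose-intensity or replacement rule may be there. This limits the finding to the readable text.

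A reader might infer that any patient reduced for toxicity in Cycle 1 passes as DLT-free, or that Part 1 is heavily biased. The documents do not support the first, for the reasons tabulated above. They do not support the second, because n and the reduction rate are not given.

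**Conclusion.** The concern holds in a narrow form. In the readable text, a Part 1 patient given all three Cycle 1 infusions, at least one below 60 mg after a related toxicity that is not a DLT, counts as evaluable and DLT-free for 60 mg. The glucose route is the clearest conflict, since one section requires leaving the dose while another exempts the event from the count. The direction is toward passing Part 1. The size cannot be computed: the illustrated falls, from 2 to 40 percentage points, rest wholly on assumed n, p and q. The conclusion assumes that no unreadable passage already settles how such a patient is classed.

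**What to change.** Change the counting rule and leave every dose and management table as it is.

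1. In the Part 1 evaluability sentence of Section 5, require that a patient counted as DLT-free completed Cycle 1 with all three copanlisib infusions at the dose under confirmation.
2. State that a patient with an adverse-event-related copanlisib reduction in Cycle 1 and no DLT is not counted as DLT-free at that dose, and name the class used. Not evaluable and replaced is the milder choice; counting against the dose is the stricter one.
3. Present the number of such patients, with the Cycle 1 doses received, beside the DLT count when Part 2 is decided. With replacement this step is essential, because replacement alone removes little of the bias (0.776 to 0.713 at n = 6, p = q = 0.15).
4. Reconcile the three-dose clause and the exemptions in Section 3.2 and the synopsis with the reduction rules in Sections 6.3.1 and 6.3.1.1.

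Redefining every Cycle 1 reduction as a DLT is not needed. Discretionary changes for Grade 1 or 2 events under Section 6.3.3 would then count toward an unchanged limit of one.

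The cost is a few sentences in an amendment. One or a few Part 1 patients may need replacing, or, under the stricter class, Part 1 becomes harder to pass, possibly by a wide margin if reductions are common.
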